5. SAMPLE SIZE

Study power is calculated using our primary outcome, seroconversion, defined as a four-fold increase in antibody titre over baseline. mRNA vaccines produce a robust immune response in over 90% of non-pregnant women/individuals.^{15,16} We will recruit 150 individuals who received a COVID-19 vaccine during pregnancy; a feasible goal based on our prior recruitment successes in the COPE Network Study and other obstetrical prospective studies.^{17,18} This will give 93% to 95% power to detect a difference in the seroconversion rate of SARS-CoV-2 neutralizing antibodies of 15% (i.e., 95% vs 80%) $\alpha=0.05$, depending on the comparison group. The sample size will also be sufficient to detect a ratio of 1.19 in the GM of antibody titres against the SARS-CoV-2 viral spike protein.^{19,20}

[figure not shown]

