3.7.4. Sample Retention

Placental biopsies and unused blood and breastmilk/chestmilk samples will be stored at the SCC for future research (e.g., placenta immunohistochemistry, metabolomic analyses). Banked samples, when paired with the detailed PLAN-V dataset will be an important resource for future research.

Objective 3 - COPE Sub-study

Comparing immune responses to COVID-19 vaccination and natural COVID-19 disease among pregnant women/individuals and their infants exposed in utero

Study design: A cross sectional analysis of maternal and infant samples at the time of delivery.

Study Population: We will use samples collected at the time of delivery from mother-infant dyads who were enrolled in the current PLAN-V study and the PI's CIHR-funded COPE Network study (CTO ID 2168).³

[figure not shown]
- **PLAN-V study participants:** Mother-infant dyads in which mothers received at least one dose of the COVID-19 vaccine in pregnancy (any type). Eligible dyads will be those where mothers had no COVID-19 infection history and from whom maternal blood and infant cord blood samples were collected at delivery (i.e., vaccinated mother-infant dyads from the pregnancy group).
- **COPE Network study participants:** The COPE Network Study is an ongoing pregnancy and birth cohort study of mothers with documented COVID-19 infection during pregnancy.³ COPE Network study participants contributed both maternal blood and infant cord blood samples at delivery. Samples from more than 100 dyads have been collected to date.

Exposures: The exposure of interest is maternal COVID-19 vaccination (PLAN-V Study) or infection (COPE Network Study) in pregnancy.

Outcome Measures: **The primary outcomes are:** seroconversion rates and antibody titres in pregnant women/individuals after COVID-19 vaccination and COVID-19 disease in pregnancy; trans-placental transfer of antibodies to neonates with *in utero* exposure to COVID-19 vaccination compared to COVID-19 disease; and differences in antibody transfer to breast/chest milk where samples are available. (Breastmilk/chestmilk samples are available from 50% of COPE Network participants). **Secondary outcomes** will be the nature and frequency of pregnancy and newborn outcomes at delivery.

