Sample analysis. Maternal and newborn cord blood serum samples collected at the time of delivery will be evaluated for SARS CoV-2 specific IgG and neutralizing antibody titres and IgG subclass distribution. Samples will be analyzed using the methods described in Section 3.7.3.

Data Sources: Immunogenicity data (including seroconversion rates and antibody titres), and data on participant characteristics (including sociodemographic information and pregnancy, delivery and newborn outcomes), will be obtained from the PLAN-V and COPE Network study datasets. The PLAN-V dataset has been purposefully aligned with that of the COPE Network Study thereby facilitating robust comparison of antibody and health outcome data. The COPE Network Study dataset includes comprehensive information on SARS-CoV-2 infection (date and gestational age of diagnosis, virus titres, symptomology, maternal and newborn case management) derived from the Ontario provincial birth registry, BORN Ontario, which has province-wide data collection on COVID-19 infection in pregnancy. The PLAN-V study data will be transferred to BORN for analysis.

Objective 4: SSO Sub-study

Comparing immune responses to COVID-19 vaccination between pregnant and non-pregnant women/individuals

Study design: A retrospective analysis of immunological data generated from two research studies

Study Population: We will use samples collected from mothers who were enrolled in the current PLAN-V study and the *Stop the Spread Ottawa (SSO)* study (OHSN: 20200481-01H; uOttawa: H-09-20-6135).³

[figure not shown]
- **PLAN-V study participants:** Women/Individuals who received at least one COVID-19 vaccine dose in pregnancy (any type). We will limit this analysis to women/individuals without known history of SARS-CoV-2 infection, and for whom maternal blood samples were collected.

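### Section 5 powers a four-fold rise over baseline, which Objective 3's delivery-only design cannot yield and which women enrolled after dose 1 cannot contribute to

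*Protocol*

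**What the plan says.** Section 5 fixes the powered endpoint: "Study power is calculated using our primary outcome, seroconversion, defined as a four-fold increase in antibody titre over baseline". It then claims: "This will give 93% to 95% power to detect a difference in the seroconversion rate of SARS-CoV-2 neutralizing antibodies of 15" percentage points, 95% against 80%, at alpha 0.05, varying with the comparison group. The recruitment target is 150. Neither the comparison groups nor the test is named.

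The Objective 3 (COPE) sub-study lists among its primary outcomes "seroconversion rates and antibody titres in pregnant women/individuals after COVID-19 vaccination and COVID-19 disease in pregnancy". Its design is "A cross sectional analysis of maternal and infant samples at the time of delivery". On the laboratory side, "Maternal and newborn cord blood serum samples collected at the time of delivery will be evaluated". The seroconversion data "will be obtained from the PLAN-V and COPE Network study datasets". The COPE group consists of mothers with documented infection in pregnancy; "Samples from more than 100 dyads have been collected to date". PLAN-V dyads qualify only if "mothers had no COVID-19 infection history and from whom maternal blood and infant cord blood samples were collected at delivery".

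For PLAN-V as a whole, Section 3.2.1 admits women who have already had one dose in the current pregnancy. Section 3.5.4 places Visit 1 before dose 1, where applicable, and Visit 2 at least 14 days after dose 1; the Table 2 notes repeat the Visit 2 timing. Section 3.7.3 gives a single-sample positivity rule (S/CO above 1.0) and plans a surrogate neutralization assay (snELISA), but links neither to the word seroconversion.

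**The concern.** A four-fold rise is a within-person ratio, so each woman needs a titre from before vaccination or infection and one from after. A single delivery sample shows whether antibody is present and how much, but not how far it has risen. If Objective 3 is run as written, one of its primary outcomes cannot be calculated by the only definition the protocol gives. A substitute would then have to be chosen after data are in hand, and the power quoted for a four-fold rise would not describe it.

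The same definition causes a smaller difficulty inside PLAN-V. A woman who joins after dose 1 has missed Visit 1. If Visit 2 served as her baseline, that titre would already reflect the vaccine and the rise would be understated, so some responders would be counted as non-responders.

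**Working it through.** **Step 1. Can the endpoint be derived?**

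| Group | Pre-exposure sample described | Post-exposure sample described | Four-fold rise |
|---|---|---|---|
| COPE mothers, Objective 3 | none | delivery | cannot be derived as written |
| PLAN-V mothers, Objective 3 | not used (delivery only) | delivery | cannot be derived from the samples used |
| PLAN-V, enrolled before dose 1 | Visit 1 | Visits 2 to 5 | can be derived |
| PLAN-V, enrolled after dose 1 | none (Visit 2 is at least 14 days after dose 1) | Visits 2 to 5 | cannot be derived |
| SSO, Objective 4 | not documented | monthly after vaccination | unknown |

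**Step 2. Reproduce the stated power.** Inputs from Section 5: 95% against 80%, alpha 0.05, 150 recruited. Assumed: a two-sided test, 126 for SSO (Objective 4 text) and 105 for COPE (the protocol says only more than 100). With pooled rate p̄ and no continuity correction:

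power = Φ{ [ |p1 − p2| − 1.96·√(p̄(1−p̄)(1/n1+1/n2)) ] / √(p1(1−p1)/n1 + p2(1−p2)/n2) }

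The corrected version subtracts ½(1/n1 + 1/n2) from |p1 − p2|.

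Worked case, 150 against 105, corrected, pregnant group at 95%:
- p̄ = (142.5 + 84)/255 = 0.888
- corrected difference = 0.15 − 0.0081 = 0.1419
- null SE = 0.0401; alternative SE = 0.0429
- (0.1419 − 1.96 × 0.0401)/0.0429 = 1.48, so power = 93.0%

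| Pregnant n | against 105 | against 126 | Test |
|---|---|---|---|
| 150 | 93.0% | 95.2% | with correction |
| 120 | 93.1% | 94.9% | without correction |

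Both rows reproduce 93% to 95%. The first counts all 150. The second corresponds to 20% of the 150 being unevaluable (150 × 0.8 = 120). The protocol does not say which applies.

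**Step 3. Effect of missing Visit 1 samples.** The share of women with a Visit 1 sample is not in the protocol, so it is assumed here. The comparator is 126, on the further assumption that SSO holds pre-dose samples. Each cell gives power with the pregnant group at 95% / at 80%.

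| Share with Visit 1 | n | With correction | Without correction |
|---|---|---|---|
| 75% | 112 | 91.4% / 91.6% | 94.2% / 94.3% |
| 50% | 75 | 81.4% / 84.7% | 87.2% / 89.2% |

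**Step 4. Why 95% against 80% needs a new justification for a positivity endpoint.** If most women in both groups are positive at delivery, the gap may be narrower. For 150 against 105 with correction, an assumed 95% against 85% gives 69.6% / 65.3%, and 95% against 90% gives 26.1% / 21.6%. These rates are illustrative; the protocol does not suggest them.

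**The case against.** Several points on the other side have force.

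- **COPE may hold earlier samples.** Section 1.2 says the network collects samples to build full infection and antibody profiles, and Objective 3 draws its seroconversion data from the study datasets. This stands as a possibility. However, COPE mothers are defined by infection in pregnancy, no pre-infection sample is described, and the Objective 3 serology is tied to delivery. The finding therefore concerns the plan as written, not what COPE's freezers contain.
- **Seroconversion in Objective 3 may simply mean positivity.** That is a sensible reading, and the PLAN-V women in Objective 3 have no infection history, so most would be expected to be negative before vaccination. But Section 5 defines the term differently and the protocol never connects it to the S/CO rule.
- **The power figure may already allow for losses.** This stands. A reader might infer from the match at 150 against about 105 and 126 that all 150 were counted and that COPE was one of the powered comparisons. The documents do not support that: 120 evaluable women and an uncorrected test fit equally well, and Section 5 names no comparator. All that can be said is that no allowance is stated.
- **The loss from missing Visit 1 samples is small.** This largely stands. It depends on an assumed share and on the test, and becomes material only if about half or more lack the sample.

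Leaving the matter to the SAP would not resolve it. The protocol itself fixes the definition, the sampling and the power, and an SAP cannot create a sample that was never taken.

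**Conclusion.** The finding holds as a mismatch between an endpoint definition and the sampling plan, and should be fixed. As written, the Section 5 endpoint cannot be derived for the Objective 3 comparison, and any of the stated 93% to 95% power intended for it does not apply. Women enrolled after dose 1 have no pre-vaccine titre, and Section 5 neither says what baseline means for them nor states an allowance.

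Confidence is high on the mismatch, which rests on the text alone. It is lower on the power consequences, which rest on an assumed 105 for COPE, assumed shares with Visit 1, an unstated test and undocumented SSO pre-dose sampling. It would be wrong to read this as an arithmetic error in Section 5, since the stated range is reproducible. Nor does it undermine the study generally: the titre, placental-transfer and milk comparisons and the Objective 4 primary outcome (titres) do not depend on a four-fold rise.

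**What to change.** 1. **Objective 3.** Replace the seroconversion rate with the proportion positive at delivery, using one single-sample rule applied identically in both groups. Positivity on the snELISA is preferable because it stays with the neutralizing antibody named in Section 5; state the cut-off that applies to it. Otherwise use S/CO above 1.0 on S/RBD and say openly that the endpoint has moved from neutralizing to binding antibody. If COPE does hold pre-infection samples and the four-fold rise is to be kept, say so and change the delivery-only text.
2. **Section 5, baseline.** Define it as the Visit 1 sample taken before dose 1, and restrict the four-fold rise to women who have that sample.
3. **Section 5, power.** Restate it for each comparison with its endpoint, test, comparator size and expected evaluable number. For Objective 3 that number should reflect the no-infection-history and paired-blood requirements. Re-justify 95% against 80% for the single-sample endpoint.

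The cost is a protocol amendment that redefines one Objective 3 primary outcome. No extra participants or samples are needed, because the delivery blood and both assays are already planned. The downside is that positivity at delivery is coarser than a four-fold rise and may sit near its ceiling, so the restated power may fall below 93% to 95%.

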6. ETHICAL CONSIDERATIONS

The study will be conducted in accordance with the Declaration of Helsinki on Ethical Principles for Medical Research Involving Human Participants, adopted by the General Assembly of the World Medical Association (2008). The study will also be conducted in accordance with the protocol, the ICH/GCP, and applicable local regulatory requirements and laws.

6.1. Research Ethics Approval

The study will be initiated by the SCC at OHRI upon the written approval of the Clinical Trials Ontario (CTO) Research Ethics Board.

- The SCC will complete the *Provincial Initial Application* and obtain ethics approval, and if applicable, ongoing renewals of the study protocol, protocol amendments, or amendments to any study documents that are required at the provincial level.
- Site Investigators/Delegates will complete the *Centre Initial Application* on CTO and obtain ethics approval, and if applicable, ongoing renewals of the study protocol, protocol amendments, informed

consent forms, and all other relevant documents (e.g., recruitment advertisements) specific to their local site. Copies of additional, local approvals, if applicable, will be forwarded to the SCC prior to the study initiation or continuation at the site.

6.2. Potential risks and benefits to participants

As an observational study, there is minimal risk to the participants and their infants. No interventions will be undertaken in connection with the project. We anticipate no adverse events associated with the study protocol. All data and samples will be collected for research purposes only.

Although there are no medical risks associated with participating in this study, participants may feel some discomfort associated with blood sample collection. Other participants may feel unease or inconvenienced with providing samples for analysis in the current or future studies, or may feel uncomfortable answering some of the survey questions. We will allow participants to choose the scope of data and sample collection at each time-point. Incomplete data or sample collection will not be an exclusion criterion for this study. To minimize burden to participants, sampling will be coordinated alongside routine clinical collections or via home-visits where possible.

There are no direct benefits to participants for taking part in this study.

6.3. Privacy and Confidentiality

All data and samples will be collected for research purposes only. Analyses will be conducted on de-identified datasets. Samples will be de-identified before being shipped to the SCC for to distribution for local laboratories for sample analysis.

[figure not shown]
Personal health information and matched unique study IDs will be kept stored on hospital/institutional approved secure networks and will be accessible only by authorized members of each participating site.

6.4. Data and Sample Management

Data and sample management will be coordinated by the SCC at the OHRI. Data and sample transfer (as well as funding and other resource transfer as needed) between the participating sites and the SCC will be governed by a contractual research agreement initiated by the SCC at the OHRI.

All data will be collected, managed and securely stored on hospital/institutional approved servers (electronic copies), or in locked offices (hard copies). The study data will be either directly captured from participants or entered by the Site Investigator/Delegate into an electronic data capture system – Research Electronic Data Capture (REDCap) – managed by the SCC at the OHRI and licensed to the Children’s Hospital of Eastern Ontario Research Institute (CHEO RI; the data custodian).

REDCap uses 128-bit data encryption, and provides role-based security requiring a user ID and password for access, facilitated by the SCC. Participants will be issued secure, web-based access to study questionnaires at the appropriate study follow-up timepoints. Site Investigators/Delegates at each participating hospital site will have access to REDCap via a unique account and password made available for each site/site user. Each site will only be able to access their site’s participant data. Data validation (range and logic checks for all variables) will be embedded where possible. Data queries will be generated and shared with study sites to ensure accuracy and completion of data. The SCC and the CHEO RI (the data custodian), will have access to all data entered in REDCap. An audit trail will be maintained for all data entry and modification. The online system (REDCap) will allow viewing the audit trail for all of the data collection forms.

Sample data will be managed separately in an encrypted file until it is merged into a single de-identified analytical file.

Research data and samples collected for this project will be archived for up to 25 years after study termination. At the end of the archival period, electronic data files will be securely deleted and any hard copies shredded. Samples will be destroyed as per institutional practices.

7. STUDY TIMELINE

We plan to conduct this research over a 2-year period. Participant recruitment, sample and data collection will begin immediately upon receipt of research ethics approval. Sample analysis will be conducted bi-weekly. Interim reports/data analysis will be completed throughout the study period.

The study timeline may be subject to changes due to duration of the pandemic, COVID-19 vaccine roll-out, and study funding.

[figure not shown]
8. KNOWLEDGE TRANSLATION

We will employ an integrated knowledge translation (iKT) strategy whereby Public Health and other Knowledge Translation partners will be involved at all project stages (design, implementation, interpretation, dissemination). The iKT plan will include strategic, traditional and patient-oriented methods of dissemination customized for patients, decision makers, clinicians and researchers.

Strategic dissemination will be achieved through regular reporting to our project partners and more broadly throughout our professional networks. The **Society for Obstetricians and Gynaecologists of Canada (SOGC)** produces clinical practice guidelines for public and medical education. SOGC has prioritized collating evidence-based information and recommendations on COVID-19 infection and vaccination in pregnancy. SOGC will review our research findings for integration into practice recommendations, and other patient and provider information tools and resources ([name]; Chief Scientific Officer). **Public Health Ontario (PHO)** works with the Ministry of Health, public health units and other health system partners to provide evidence and expertise that will support COVID-19 efforts. This includes providing scientific advice, resources and surveillance to support implementation of COVID-19 vaccine programs. PHO partners have committed their scientific expertise to the study ([name]; infectious disease epidemiology, vaccine coverage and program evaluation) and will support timely integration of findings into evidence briefs ([name]; Chair, Health Growth & Development Evidence Network). The **BORN Ontario** birth registry manages accurate and reliable reproductive data for population health surveillance and program/service planning to improve Ontario's maternal child health system²¹. BORN is coordinating province-wide data collection on COVID-19 infection in pregnancy and will be conducting provincial vaccine safety surveillance. BORN will provide their technical and scientific expertise toward the study design, and support knowledge dissemination. ([name]; Scientific Director). At the local level, **the Champlain Maternal Newborn Regional Program (CMNRP)** will help advertise the study to the public, and disseminate our findings by hosting webinars, and distributing educational materials.

Among our team, we also have direct access to vaccine and maternity care authorities including the **National Advisory Committee on Immunization (NACI)** ([name], [name]) and the **Ontario Provincial Council for Maternal and Child Health Maternal-Neonatal COVID-19 Task Force** ([name]).

Traditional dissemination will occur in the form of peer-reviewed publications and scientific presentations targeted at clinicians and researchers. To ensure optimal impact we will apply open science best practices across

all aspects of the research program.^{22–24} Where possible, anonymized data will be shared at the end of the program.

Public dissemination will be achieved through a combination of traditional and social media platforms. Public dissemination will be informed by **Patient Partners**. The COPE Network research hub in Ottawa runs a **Patient Partner Program** designed to integrate the experiences of pregnant women/individuals throughout the research process. We have found this to improve the quality of research, knowledge transfer, and advance patient care. All technical reports and scientific publications will be accompanied by **lay summaries** to ensure that our messaging is clear and easily understood. We will leverage **in-house communication/media support** to draft press-releases as the project achieves key milestones, so that these can be shared with the public.

A **dedicated project website** will document recruitment progress and host all technical reports, publications, presentations and lay summaries.

[figure not shown]

10. RELEVANCE AND IMPACT

This study will build on existing projects and infrastructure to provide insight into the impact on vaccine timing, dosing and type on immunogenicity and safety of COVID-19 vaccination in the maternal-newborn population, and placental antibody transfer to newborns. Our findings will be informative for knowledge-users and policy-makers on COVID-19 vaccination and support informed decision-making about COVID-19 vaccination for new and expectant Canadian families. Finally, this work will lay the foundation for longer-term follow-up studies of maternal and pediatric health outcomes after COVID-19 vaccination in pregnancy and the pivotal role of maternal vaccination for protection of newborns.

